# 2 Relevant Abbreviations

ADE	A.1. D	LIZD	T 1 1 771 1 1
ADE	Adverse Device Effect	LKP	Leiter der Klinischen
AE	Adverse Event		Prüfung/Lead Coordinating
ALT	Alanine transaminase		Investigator
AST	Aspartate transaminase	MCB	Multi-chamber bags
BfArM	Bundesinstitut für Arzneimittel	mGPS	modified Glasgow
	und Medizinprodukte		Prognostic Score
BMI	Body Mass Index	MPG	Medizinproduktegesetz
BSI	Bloodstream infections	NI	Nutritional intervention
CC	Cancer anorexia-cachexia	NRS	Nutritional Risk Screening
CLABSI	Central line-associated	OS	Overall survival
	bloodstream infections	PN	Parenteral nutrition
COM	Compounded bag	PP	Per protocol
CRBSI	Catheter related	QoL	Quality of life
	bloodstream infection	SAP	Statistical analysis plan
CRP	C-reactive protein	SAS	Statistical Analysis System
CRI	Catheter Related Infection	SmPC	Summary of Product
CTC	Common toxicity criteria	Sim C	Characteristics
ECOG	Eastern Cooperative Oncology	WHO	World Health Organization
Leod	Group	WIIO	World Hearth Organization
EDC	Electronic data capture		
EOT	End of treatment		
(e)CRF ESPEN	(electronic) case report form		
ESPEN	European Society of Parenteral		
CCD	and Enteral Nutrition		
GCP	Good Clinical Practice		
GMP	Good Manufacturing Practice		
GOT	Glutamic oxaloacetic		
~ ~	transaminase		
GPT	Glutamate-pyruvate		
	transaminase		
HPN	Home parenteral nutrition		
HPN-PROQ	Home parenteral nutrition		
	Patient-reported outcome		
	Questionnaire		
ICH	International Council for		
	Harmonisation		
IDMC	Independent Data Monitoring		
	Committee		
IIT	Investigator-initiated trial		
IRB	Institutional Review Board		
ISF	Investigator site file		
ITT	Intent-to-treat		
IWRS	Interactive Web Response		
11110	Systems		
LDH	Lactate dehydrogenase		
בוטוו	Lactate deligatogenase		

-CONFIDENTIAL- Page 6 of 33

To avoid misunderstandings, the following terms shall be clarified: In the context of this study, the term "standard PN" refers to the standard composition of the PN. The 2/3-chamber bags, that have been used in clinical routine for decades (industrially manufactured bags as well as pharmacy-compounded bags) will be referred to as "traditional" bags, that will be tested vs. Eurotubes®.

#### 3 Background and rationale

#### 3.1 The medical problem

Cancer is often characterized by extensive invasion, early metastases, and, in many cases, a rapidly occurring marked cachexia leading to a very limited prognosis especially in the metastatic situation.

Cachexia is a strong and independent predictor of mortality, poor therapeutic response, diminished functional capacity, and reduced quality of life (QoL). It is defined as the debilitating state of involuntary weight loss, often connected with anorexia, tissue wasting, malnutrition, and inability for natural nutrition intake. The combination of these symptoms, also characterized by systemic inflammation, is also named "cancer anorexia-cachexia syndrome" (CC) [Vanhoutte et al., 2016; Fearon et. al, 2011]. The most important phenotypic feature is muscle wasting and functional impairment as a result of increased protein degradation and reduced protein synthesis or both [Bossola et al., 2007]. The syndrome is life-threatening and debilitating for approximately 50% of all cancer subjects [Bossola et al., 2007].

As reported, the QoL is significantly impaired in CC subjects and there is evidence for increased morbidity and mortality of subjects with CC [Bossola et al., 2007]. Subjects suffering from CC commonly have derangements in basal metabolic rate as well as reduced appetite and food intake. Even moderate weight loss is associated with psychological stress and lower QoL. Furthermore, CC affects subject's response to chemotherapy [Bossola et al., 2007].

Malnourished patients are more difficult to guide through chemotherapy experiencing more severe side effects resulting in progressive cachexia. The outcomes of subjects with CC receiving chemotherapy can be improved with nutritional intervention (NI) [Bauer and Capra, 2005]. Supplementation with parenteral nutrition (PN) improves the QoL in subjects with advanced CC. There is also data indicating that NI has a synergistic effect with anti-cancer

-CONFIDENTIAL- Page 7 of 33

therapy and results in better clinical outcome [Ravasco et al., 2005a; Ravasco et al., 2005b; Bauer and Capra, 2005; Caccialanza R. et al., 2018].

The European Society of Parenteral and Enteral Nutrition (ESPEN) recommends PN only for malnourished subjects but does not reflect the situation in CC patients. Nevertheless, PN has become a standard of care in cancer patients who are not able to maintain their weight or who are at risk of suffering cachexia. PN is now widely accepted as an important component of cancer patients' treatment in the oncology community and is covered by the patients' insurances.

Despite recent advances in PN for cancer, several clinical problems are still unresolved:

- 1. Patients receiving PN are dependent on home nursing service, which represent a major limitation of their autonomy and quality of life.
- 2. Patients receiving PN are at high risk of developing blood stream infections.
- 3. The potential benefit of reduced glucose levels and in the consequence higher levels of fat is a long-lasting question that has not been evaluated yet.

#### 3.2 Background and Rationale

Approximately 50% of all cancer subjects suffer from CC and its severe impact on QoL and response to chemotherapy [Bossola et al., 2007]. Especially in the advanced stages, it cannot be fully cured by increased food intake or oral supplements and requires supportive or total parenteral nutrition. If needed, patients can live on PN for an unlimited time, the mean administration period varies depending on the underlying disease and the patient's general condition. However, the change from oral food intake to PN is associated with many changes in the subject's everyday life that lead to restriction of autonomy and flexibility. CC patients are often unable to handle the connection and disconnection of the nutrition bags to their catheter correctly on their own, especially when supplements need to be added. Nursing services need to visit the subject daily to perform the PN administration. The infusion takes around 12 to 14 hours to finish and is typically administered in the evening to be infused overnight. The subjects' daily life is highly determined by the appointments of the nursing service, overnight stays away from home are nearly impossible and the dependency on outside assistance can diminish the patients' self-esteem and QoL. The extent to which these limitations to the subject's self-determination impact the QoL is currently poorly studied and needs further

-CONFIDENTIAL- Page 8 of 33

investigation. Subsequently, it is of high interest to assess if the QoL shows to be higher in subjects performing the PN administration autonomously without nursing service assistance.

Furthermore, data has shown that PN is accompanied by an increased risk of blood stream infections (BSI) [Dissanaike et al., 2007] and is an independent risk factor for both catheter-related bloodstream infections (CRBSI) and central line-associated bloodstream infections (CLABSI) [Beghetto et al., 2005]. BSI represent 15% of all nosocomial infections and are associated with increased mortality and other serious medical conditions such as severe sepsis or septic shock [Pontes-Arruda et al., 2012]. In addition to the safety aspect, BSI lead to longer hospital stays and hence, additional costs [Turpin et al., 2011].

Although most PN related BSI are caused by the intravenous catheter, numerous manipulations on the infusion unit may multiply the hazard of extrinsic contaminations [Didier et al., 1998].

To reduce this well-known risk, the relevant phases of PN (production, adding of supplements, administration) are subject to highest standards of hygiene in order to minimize the contamination risk. Industrial PN is manufactured following the guidelines of Good Manufacturing Practice (GMP) and under clean room conditions which reduces the contamination hazard significantly. Data indicate advantages of industrially manufactured PN compared to pharmacy-compounded PN formulations in terms of safety, however the limited data do not allow a definite conclusion [Turpin et al., 2012].

Blood glucose levels and ketogenic diets are a contentious issue and subject of controversial discussion among oncologists. In the 1920s, Nobel laureate Otto Warburg observed that unlike healthy body cells, cancer cells strongly upregulate the glucose intake to produce energy preferably via glycolysis, instead of the much more efficient way of oxidative phosphorylation [Liberti and Locasane, 2016]. This phenomenon is known as the Warburg-Effect. Data prudently suggest that carbohydrate restriction and ketogenic diets possibly obstruct cancer growths [Klement and Kaemmerer, 2016], however, too few clinical data is available to come to a definite conclusion. Due to the low level of evidence, the ESPEN guidelines 2017 encourages further research on the effect of high fat diets on clinical outcome in patients with systemic inflammation and generally the effect of varying the fat [ESPEN guidelines, 2017, p. 21].

-CONFIDENTIAL- Page 9 of 33

#### 3.3 Parenteral nutrition

Parenteral nutrition is a sterile, liquid formula that is administered through an intravenous catheter directly into the bloodstream. It bypasses the normal digestion of the gastro-intestinal tract and may contain all necessary nutrients such as carbohydrate, protein, fat, electrolytes, (trace) minerals and vitamins. Various diseases and conditions that impair food intake or nutrient absorption may require the partial or complete substitution of oral or enteral nourishment. Patients who underwent acute surgery, suffer from short bowel syndrome or gastro-intestinal fistulas as well as critically ill patients including cancer patients at risk of CC may (temporarily) depend on PN. The specific composition needs to be customized to the individual needs of the patient depending on several factors as age, height, weight, nutritional requirements, underlying disease and the ability to intake enteral nutrition.

The most common product types used in parenteral nutrition are either industrially premixed multi-chamber (2/3-chamber) bags or pharmacy-compounded admixtures in a mono- or 2-chamber bags. The third, latest development are 7-, 8- or 9-chamber bags (Eurotubes®).

#### 3.3.1 Traditional 2/3-chamber bags

Traditional 2/3-chamber bags are widely used in the PN landscape. Two or three separate compartments provide a combination of amino acids, lipids, glucose and electrolytes. Typically, most supplements cannot be added to the premixed 2/3-chamber bags due to stability reasons and incompatibilities. Also, the individual requirements vary significantly. To fully meet the patients' needs, additional substances and agents are injected via syringe into the infusion unit shortly before administration of the product. That causes extra steps within the preparation process and increases the risk of errors and contamination. In patients receiving PN at home, that final step is usually performed by the nursing service, a family member or the patient himself. It is critical to perform this procedure in an environment as sterile as possible to avoid contamination of the product.

The industrially premixed formulation can be stored at room temperature for several months and is available in different admixtures to meet various patients' needs. However, the addition of vitamins, drugs or other supplements shortly before administration is always necessary if the composition of the industrially manufactured bags do not meet the individual requirements, which is frequently the case.

-CONFIDENTIAL- Page 10 of 33

#### 3.3.2 Pharmacy-compounding

The on-demand compounding comprises another possibility to customize the PN formulations and provide the optimal composition of all needed supplements and medical agents. Pharmacies or commercial compounding services offer the PN customization on-demand and deliver the required infusion units. If there are no restrictions in compatibility, stability and/or storage then as many substances as possible can be combined. However, at least the addition of vitamins still needs to be performed and the problem of additional manipulations before administration remains.

#### 3.3.3 Eurotubes®

Eurotubes® have been developed in 2013 to offer fully individualized PN compounding under GMP standard without the need for further line or bag manipulation outside the controlled GMP environment.

Depending on the patient's nutritional requirements the PN's composition may be considerably complex. Besides trace minerals, extra electrolytes and vitamins, additional medications may be necessary. The 7-,8- or 9-chamber bags provide six extra compartments to separately add further substances such as vitamins or pharmaceuticals in the needed quantity and without the risk of instability or incompatibilities. They are customized to the individual recipient and contain all prescribed nutrients or medical agents in a ready-to-use system. After mixing the individual compartments, the infusion unit is ready to be used without further preparation. The system can also be equipped with an integrated pump feeding set which is ventilated and does not require further manipulations. Depending on the patient's general condition, it is easily possible to self-administer the bags without the assistance of a nursing service or family member. The subjects' daily routine stays independent from the nursing service, which is presumed to increase personal independence and flexibility while decreasing the overall treatment costs.

#### 3.4 Studies on parenteral nutrition and infection

To the present day, multiple studies have been conducted comparing industrially manufactured bags versus pharmacy-compounded bags to investigate the correlation of CRBSI and PN in subjects malnourished due to various reasons, including but not limited to cancer anorexia cachexia. It has been sufficiently demonstrated that PN is associated with an increased hazard of CRBSI, consequently with a prolonged hospital stay and thus, with higher costs.

-CONFIDENTIAL- Page 11 of 33

Pontes-Arruda et al. [Pontes-Arruda et al., 2012] compared industrially pre-mixed PN products to individually compounded bags (COM-group, fabricated either by the hospital's pharmacy or a compounding service provider) in 403 patients in total. The subjects of the COM-group showed a higher incidence of BSI and CLABSI than the subjects receiving industrially pre-mixed PN (BSI: 22,5 % vs. 16,8 %, p = 0,03 and CLABSI: 13,2 % vs. 10,3 % per 1.000 catheter days, p < 0,0001). This suggests an advantage in terms of safety of PN products that are manufactured under GMP standards, however the study neglects to investigate the individual contamination risks in all occurring phases (production, compounding, injection of supplements, administration) and consequently cannot isolate the primary source of the infections.

Pounds et al. [Pounds et al., 2013] showed in a single center trial that subjects treated with pharmacy-compounded PN experienced more adverse drug reactions and metabolic abnormalities than subjects receiving premixed parenteral nutrition. 18% of the COM-group developed a severe sepsis vs. 12% in the comparator arm, however, the sample size of 50 patients per cohort limits the significance and requires further investigations.

The review of Turpin et al. [Turpin et al., 2014] evaluated the impact of parenteral nutrition preparation on BSI risk and costs in 1.995 patients in Germany and brings an interesting angle into the investigations: He evaluated the risk of BSI and the cost of PN by retrospectively reviewing data of patients receiving PN via either multi-chamber bags (MCB), single bottle or hospital compounded admixtures and correlated the type of PN to the hospital costs. In his research he also discovered that adding supplements to MCB on the ward almost doubles the BSI hazard (rate of BSI per 1.000 PN days in MCB without additions vs. with addition: 4,3 vs. 8,5). These data suggest that the quantity of manipulations and injections at the infusion unit correlates with the number of BSI and associated Adverse Events. However, further prospective, randomized trials will be needed to confirm this implication.

#### 3.5 Rationale for PEKANNUSS trial

PN at home using traditional 2/3-chambers is associated with a significant limitation and burden to the patients, as they are dependent on home care and nursing for administering the PN and injection of the required nutrition compounds. PN is, therefore, associated with frequent manipulation at the peripheral or central intravenous device. Data indicate that less manipulation on the PN bags before actual application to the patient reduces the hazard of BSI, however, industrially premixed MCB are often unable to entirely meet the patients' needs and

-CONFIDENTIAL- Page 12 of 33

require additional injections of supplements. Multiple line manipulations are required to substitute several nutrition compounds, leading to a high risk of catheter related complications, and limiting subjects' autonomy. Eurotubes® – as ready-to-use system – require less manipulations and are, therefore, expected to be associated with less complications. The Eurotubes® are already used in the clinical routine practice. However, there is no clear recommendation which type of bags should be used in cancer patients, as there are no clinical trials comparing Eurotubes® versus traditional bags with regards to safety, QoL and response to concomitant anti-cancer therapy. Therefore, further research with randomized controlled trials is urgently required.

#### 3.6 The relevance of this study to current care and benefit-risk assessment

As elaborated above, the CC patients could benefit from a higher QoL by preserving the subjects' autonomy and ability to self-administer the PN infusions.

Furthermore, CRI represent a serious complication in patients receiving PN, weakens the already impaired subject, potentially delays chemotherapy and thereby diminishes therapeutic success. If the Eurotubes® prove to be efficient in preventing CRI, PN could become safer, more efficient and hospitalization time could be abbreviated.

The procedures used in this study (such as PN application, blood tests, use of a patient's study diary and QoL questionnaires) are in line with the current standard of care or minimal interventional, respectively. 2/3-chamber bags and Eurotubes® used for PN are market-approved infusion units with no experimental approach.

There is no evidence of a negative impact of glucose-reduced nutrition on CC subjects and can therefore be tested for its potential inhibitory effect on tumor growth.

Taken together, the risks emerging from participation in this clinical trial are acceptable, considering the anticipated direct benefits for a subset of patients and the impact of the study results on the future treatment of patients in the given indication.

-CONFIDENTIAL- Page 13 of 33

#### 4 Study design

This is an open-label, randomized, multicenter, investigator-initiated, phase IV trial. A total number of 216 patients will be enrolled (see chapter 7 for statistical calculations).

Patients with metastatic or localized solid tumors who fulfil the eligibility criteria and who have an indication for parenteral nutrition will be enrolled.

Patients will be stratified according to ECOG (0-1 vs. 2 vs. 3), the modified Glasgow Prognostic Score (mGPS) (0-1 vs. 2) and whether the patient receives concurrent systemic anti-cancer treatment (e.g. chemotherapy, targeted therapy, immunotherapy) or not.

In a first step, patients will be randomized in a 2:1 ratio to Arm A or Arm B:

Arm A: Standard Parenteral Nutrition using Eurotubes®.

or

#### Arm B: Standard Parenteral Nutrition using 2/3-chamber bags.

Patients randomized to Arm B will receive PN according to the routine used by the participating site.

Patients in Arm A will be stratified again by the same criteria as listed above and randomized in a 1:1 ratio to Arm A-1 or Arm A-2:

#### Arm A-1: Standard Low Glucose Parenteral Nutrition using Eurotubes®.

Patients randomized to Arm A and in a second randomization to treatment Arm A-1 receive PN reduced in glucose in Eurotubes®.

or

# **Arm A-2**: Standard Parenteral Nutrition using Eurotubes®.

Patients randomized to Arm A and in a second randomization to treatment Arm A-2 will receive standard PN in Eurotubes®.

Patients will be recruited during regular consultation visits.

An overview of the study scheme is given in Figure 1.

-CONFIDENTIAL- Page 14 of 33

[figure not shown]

Figure 1: Study Scheme.

-CONFIDENTIAL-

At screening and at all regular visits during the HPN treatment period (one visit per four-week interval after randomization for a maximum of 12 months) the ECOG performance status and body weight will be determined. Additionally, physical examinations and laboratory assessments including CRP, albumin and total protein levels will be performed. Laboratory assessments do not need to be repeated at screening if laboratory assessments were done prior to screening within clinical routine and results are not older than 2 weeks. The type of catheter used for parenteral nutrition will be documented (Port-a-Cath, Hickmann/Broviac catheter etc).

The HPN therapy and any modifications and adjustments to this plan during the course of HPN treatment will be recorded from visit 1 onwards.

Anti-cancer treatment at the time of screening and any changes during the course of the HPN treatment period (e.g. type of treatment) will be documented.

Monitoring of Adverse Events and medical device deficiencies will be performed at every visit. AEs will be graded according to the National Cancer Institute's Common Terminology Criteria for Adverse Events (NCI CTCAE) version 5.0.

During the study the patient will maintain a study diary to document details of the administration of the HPN. A QoL questionnaire will be completed during regular study visits until EOT.

After completion of study treatment, patients will enter the follow-up period. During this period, they will be followed approximately every 3 months for survival which can be done by phone.

-CONFIDENTIAL- Page 16 of 33

#### 5 Objectives and Endpoints

#### 5.1 Objectives

#### 5.1.1 Primary objective

#### Patient autonomy

To compare the frequency of self-administered parenteral nutrition at home (HPN) (autonomy rate) in patients with metastatic or localized solid tumors receiving standard parenteral nutrition through Eurotubes® versus traditional 2/3-chamber bags in the intent to treat population (ITT).

#### 5.1.2 Secondary Objectives

#### Secondary Objectives

- To compare the incidence of catheter related infections (CRI) between treatment Arms A and B in the per protocol population.
- To compare the efficacy of PN in terms of body weight, C-reactive protein (CRP) and albumin levels, and overall survival (OS)
- To compare the Quality of life (QoL) by use of the MODIFIED HPN-PROQ questionnaire
- To determine the frequency of PN-related visits by the nursing service
- To compare the safety in terms of the incidence of other catheter related complications, severe, common toxicity criteria (CTC) grade 3-5 infections, and PN-related Adverse Events (AEs)

#### Secondary Objectives (Arm A-1 vs. A-2)

- To compare the incidence of catheter related infections (CRI)
- To compare the efficacy of PN in terms of body weight, C-reactive protein (CRP) and albumin levels, and overall survival (OS)
- To compare the Quality of life (QoL) by use of the MODIFIED HPN-PROQ questionnaire
- To compare the safety in terms of the incidence of other catheter related complications, severe, common toxicity criteria (CTC) grade 3-5 infections, and PN-related Adverse Events (AEs)

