#### 5.2.2 Secondary endpoints

#### Efficacy endpoints

- Relative weight change determined at baseline and during study visits approx. every four weeks after enrolment;
- Relative change of albumin and CRP levels measured at baseline and during regular study visits;
- Overall survival (OS) defined as the time from randomization to death from any cause.

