#### 6.3.2 Statistical methods for the analysis

#### Patient Demographics/Other Baseline Characteristics

The following demographic and baseline characteristics will be summarized descriptively by treatment group:

- Gender and age;
- Patients' disease (e.g. colon cancer, breast cancer, gastric cancer);
- Tumor status (localized or metastatic solid tumors);
- Number and type of organs involved in metastatic disease (e.g. liver, lung, lymph nodes, bone);
- Patients history (concomitant disease, number and type of previous anti-cancer therapies);
- Type and start date of the current/concomitant anti-cancer therapy;
- ECOG performance status;
- mGPS
- Nutrition risk screening score;
- Baseline lab values and baseline QoL;
- Other characteristics.
- Type of central catheter used for parenteral nutrition

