#### 7.2 Exclusion Criteria

Patients who meet any of the following criteria will be excluded from study entry:

- 1. > 4 weeks of consecutive (3  $\ge$  days per week) parenteral nutrition in the last 3 months prior to study enrolment
- 2. Participation in another interventional clinical trial that could influence the endpoints of this trial or planned participation in such a study at the same time as this study is active (participation in other trials is possible in the follow up time for OS). The study is active, if the patients receive study treatment (PN), did not discontinue the trial for other reasons, and is still within the 12 months active study period
- 3. Current catheter related infection at baseline. In patients with a suspected/proven previous conservatively managed catheter-related infection, a negative pair of blood cultures drawn from the central catheter is required.
- 4. Pregnancy or breastfeeding
- 5. Known hypertriglyceridemia ≥ CTCAE grade 3
- 6. Unable or unwilling to provide written informed consent and to comply with the study protocol
- 7. Uncontrolled diabetes mellitus
- 8. Congestive heart failure NYHA  $\geq$  3
- 9. Renal insufficiency GFR < 30 ml/min
- 10. Uncontrolled infection
- 11. Liver insufficiency

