**Table 1: Schedule of Assessments** 

Schedule of Assessments	Screening	Visit 1 – Visit 12¹	EOT Visit	Follow- Up 
Informed consent 	X			
ECOG	X 	X	$X^{16}$	
Modified Glasgow Prognostic Score (mGPS)	$X^4$	X	X	
Nutritional Risk Screening	X 			
Physical Examination	X	X	$X^{16}$	
Weight	X	X	$X^{16}$	
Height	X			
Medical History	X			
Demographics, other baseline parameters	X			
Concomitant anti-cancer therapy (if any)	X 	$X^6$	$X^6$	
Laboratory 	X	X	X	
Pregnancy test 	X			
Catheter Related Infections (CRI)	X	X	X	
Any catheter related complications	X	X	X	
Adverse Events 	X	X	X	(X)
Medical device deficiencies 		X	X	
QoL questionnaire 	X	X	$X^{16}$	
Patient's study diary	$X^{12}$	$X^{13}$	$X^{13}$	
HPN therapy plan / administration/documentation		X 	X 	
Post discontinuation PN				$X^{15}$
Overall survival		X	X	X

- (1) A maximum of 12 visits should be documented within the study. The visit schedule itself is up to the clinical routine at the site and may occur approx. every four weeks. However, only the first visit within each four-week interval (starting from randomization) will be documented. If there is more than one visit within a four-week interval, only the first visit will be documented.
- (2) Every 3 months (+/- 2 weeks) until death or end of the study for survival status.
- (3) Mandatory prior to any study procedure.
- Should be (re-)determined by the study personnel even if known through the documentation received by the inpatient facility. Please note: ECOG PS of 0, 1, 2 and 3 are eligible for the trial.
- (5) Any anti-cancer therapy (including surgery and radiation) should be documented.
- (6) Changes in the anti-cancer therapy should be documented
- (7) Routine peripheral blood lab usually done in patients receiving HPN including but not limited to: Complete blood count (German: kleines Blutbild), albumin, total protein level (German: Gesamteiweiß), CRP, GOT (AST), GPT (ALT), LDH, cholinesterase, creatinine, triglycerides, urea, glucose, electrolytes (sodium, potassium, magnesium, calcium, phosphate) should be

-CONFIDENTIAL- Page **30** of **33** 

- determined according to local lab routine. Laboratory assessments do not need to be repeated at screening if laboratory assessments were done prior to screening within clinical routine and results are not older than 2 weeks.

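### Triglycerides, liver enzymes, glucose and electrolytes are scheduled throughout treatment but have no planned analysis after baseline, so the metabolic safety of low-glucose PN rests on adverse event recording in an open-label trial

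*Combined protocol and SAP*

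**What the plan says.** All places are in the combined protocol and SAP.

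- **What is measured.** Footnote 7 to Table 1 (section 9.1) lists the routine blood tests, among them "GOT (AST), GPT (ALT), LDH, cholinesterase, creatinine, triglycerides, urea, glucose, electrolytes (sodium, potassium, magnesium, calcium, phosphate) should be" determined by local laboratory routine. The laboratory row of Table 1 is marked at screening, Visits 1 to 12 and EOT. Footnote 1 adds: "A maximum of 12 visits should be documented within the study", and only the first visit in each four-week interval is documented.
- **What is analysed after baseline.** Section 5.2.2 lists one laboratory endpoint, under efficacy: "Relative change of albumin and CRP levels measured at baseline and during regular study visits".
- **What is summarised at baseline.** Section 6.3.2 mentions other laboratory values only as "Baseline lab values and baseline QoL".
- **Safety endpoints (5.2.2).** Catheter related infections, catheter complications, severe infections and other CTC-graded adverse events, PN-related adverse events, and hospitalizations. None is a laboratory measure.
- **Safety objective for A-1 against A-2 (5.1.2).** Other catheter complications, "severe, common toxicity criteria (CTC) grade 3-5 infections, and PN-related Adverse Events (AEs").
- **Adverse event capture.** Footnote 9 to Table 1 captures events whether or not they are related, from consent to 14 days after the last study treatment. Section 4 describes the trial as open-label.
- **Why fat matters here.** Section 3.1 says: "The potential benefit of reduced glucose levels and in the consequence higher levels of fat is a long-lasting question". Section 7.2 excludes patients with "Known hypertriglyceridemia ≥ CTCAE grade 3".

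**The concern.** A-1 against A-2 is the trial's only randomized test of low-glucose PN. If less glucose means more lipid, triglycerides and liver enzymes are obvious values to compare, and glucose and electrolytes belong beside them. The schedule collects all of these, but no endpoint, grading rule, shift table or comparison by arm uses them after baseline.

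The results then depend on who records what. An abnormal value that causes no symptoms becomes data for the safety tables only if the investigator enters it as an adverse event. The investigator knows the arm, and the document gives no rule for when a laboratory abnormality must be recorded as an event. The adverse event tables could therefore look alike in the two arms while the laboratory values differ, and nothing in the listed analyses would show it.

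**Working it through.** **1. Schedule against analysis.** Footnote 7 names 17 items, counting the blood count as one and the five electrolytes separately. Table 1 allows up to 1 + 12 + 1 = 14 occasions per patient (screening, Visits 1 to 12, EOT). Two of the 17 items, albumin and CRP, have an endpoint after baseline. For the metabolic items the comparison is:

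| Measure | Scheduled after baseline | Analysis listed after baseline |
|---|---|---|
| Albumin, CRP | yes | relative change, efficacy |
| Triglycerides | yes | none |
| GOT, GPT | yes | none |
| Glucose | yes | none |
| Electrolytes | yes | none |

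**2. How wide the adverse event route is.** The objective in 5.1.2 names PN-related events. Section 5.2.2 adds other CTC-graded events and hospitalizations, and footnote 9 captures events regardless of relatedness. A metabolic event not attributed to PN can therefore still be counted. Relatedness does not gate the whole route, but the decision to record an event does.

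**3. Does A-1 imply more fat?** Inputs from section 8:
- glucose 1.0 to <2.0 g/kg in A-1 and 2.0 to 4.0 g/kg in A-2;
- amino acids 1.2 to 1.5 g/kg in both, midpoint 1.35;
- total 25 to 30 kcal/kg in both;
- 4, 4 and 10 kcal per g of glucose, amino acids and lipid;
- lipid range 0.5 to 2.0 g/kg printed for both arms.

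Formula: lipid (g/kg) = (total kcal/kg − 4 × glucose − 4 × 1.35) / 10.

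| Total kcal/kg | Glucose g/kg | Calculation | Lipid g/kg |
|---|---|---|---|
| 25 | 1.0 (A-1, low end) | (25 − 4 − 5.4)/10 | 1.56 |
| 25 | 2.0 (A-1 upper limit, A-2 lower limit) | (25 − 8 − 5.4)/10 | 1.16 |
| 25 | 4.0 (A-2, high end) | (25 − 16 − 5.4)/10 | 0.36 |
| 30 | 1.0 | (30 − 4 − 5.4)/10 | 2.06 |
| 30 | 2.0 | (30 − 8 − 5.4)/10 | 1.66 |
| 30 | 4.0 | (30 − 16 − 5.4)/10 | 0.86 |

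Implied lipid is thus about 1.2 to 1.6 g/kg (A-1) against 0.4 to 1.2 g/kg (A-2) at 25 kcal/kg, and about 1.7 to 2.1 against 0.9 to 1.7 g/kg at 30 kcal/kg. At equal calories and amino acids the difference is 0.4 × (glucose in A-2 − glucose in A-1). It runs from about 0.4 × (2.0 − 2.0) = 0 to 0.4 × (4.0 − 1.0) = 1.2 g/kg.

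Two corner values, 0.36 and 2.06, fall just outside the printed lipid range, so the ends of this range are outer bounds.

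**The case against.** **A later SAP can supply this.** Section 6.3 says the SAP will be completed before any analysis, and sections 6.3.1 and 6.3.2 leave further details to it. Routine laboratory tables could properly appear there, and the present text cannot show that they will be left out. That stands, and it makes this a gap to close rather than an error. But the document already lists its safety endpoints and laboratory values are not among them. A general deferral does not supply measures or a grading rule.

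**Adverse events already cover it.** A reader might infer from the objective that metabolic harm counts only if judged PN-related. The documents do not support that, as step 2 shows. What remains is dependence on unblinded recording.

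**The protocol does not identify metabolic harm as specific to A-1.** This also stands in part. Section 3.6 states that there is no evidence of a negative impact of glucose-reduced nutrition. The exclusions in 7.2 and the refeeding caution in section 8 apply to every arm. The single-center study in section 3.4 that found more metabolic abnormalities compared pharmacy-compounded with premixed PN. A-1 and A-2 use the same bag, so that study does not bear on this contrast. The support is section 3.1 and the calorie arithmetic.

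**The fat contrast may be small.** A reader who takes the midpoint of each range would infer a fixed, substantial excess of fat in A-1. The glucose ranges meet at 2.0 g/kg, both arms print the same lipid range, and section 8 lets composition depart from the tables. Only a range can be stated.

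**Lost power and a false safety claim.** It is tempting to express the gap as lost power, but the documents give no event rates or recording fractions, and section 6.3.2 makes secondary p-values descriptive. Nor does the plan intend to declare the arms equally safe: it contains no equivalence or non-inferiority claim.

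**Conclusion.** The concern holds as a gap in the listed analyses. Triglycerides, GOT, GPT, glucose and electrolytes are scheduled on up to 14 occasions per patient, yet no analysis after baseline is listed for them. Followed as written, the metabolic safety of low-glucose PN reaches the results only through events that unblinded investigators choose to record, although that route takes in all CTC-graded events, related or not.

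The implied lipid difference is about zero to 1.2 g/kg per day. This assumes that the calorie guidance is followed, with equal calories and 1.35 g/kg amino acids in both arms. The true contrast is unknown. The documents do not show that A-1 is harmful or that events will be under-recorded. They show that the plan has no listed means of detecting a laboratory difference independently of adverse event recording. The primary endpoint is not affected. This is a worthwhile, inexpensive improvement.

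**What to change.** Add to the safety endpoints in 5.2.2 and to the methods in 6.3.2, and name in the A-1 against A-2 safety objective in 5.1.2, wording such as:

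> In the safety set, triglycerides, GOT, GPT, glucose, potassium, magnesium and phosphate from documented visits are graded by CTCAE v5.0 or by local reference limits, independently of adverse event reporting. The worst documented post-baseline grade, the shift from baseline and the proportion with a newly abnormal value are presented for A-1 against A-2 and for A against B, with risk differences and 95% confidence intervals for proportions. The analysis is descriptive.

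State for each measure which of the two grading scales applies. Keep the adverse event tables as they are. Fix the wording before the interim analysis planned after 100 patients (section 6.3), so that measures and grading are not chosen with data in view.

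**Cost.** No new visits or blood tests, and no change to clinical management. Laboratory values and local reference ranges must be entered in the eCRF. The footnotes to Table 1 state transcription for the questionnaire and the diary but not for these values, so this may be extra work for sites. There will be more descriptive comparisons. Values from undocumented visits will be missed, so the worst grade is the worst documented one and should be labelled that way.
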